## Abstract

Stroke is the leading cause of serious, long-term disability. The emergence of abnormal muscle synergies following a stroke presents a major limitation to the recovery of independent function. Despite the development of many interventions for movement recovery post-stroke, rehabilitation treatments are minimally effective to muscle synergy impairment. Treatment advances have been hampered by our poor understanding of neural plasticity post-stroke and the overall lack of precise interventions in neurorehabilitation. Thus, our long-term objectives are to 1) improve the understanding of the underlying neurobiological mechanism of neural plasticity that drives the recovery of motor function; 2) develop targeted interventions that improve stroke rehabilitation in more impaired individuals. Our previous studies have found that muscle synergy impairment is associated with the damage to the corticospinal tract and the maladaptive recruitment of contralateral cortico-reticulospinal tract. We hypothesize that facilitating the damaged cortico-spinal tract (via primary motor cortex) and/or inhibiting the contralateral cortico-reticulospinal tract (via dorsal premotor cortex) will reduce muscle synergy impairment and improve upper extremity motor function. In this OSCTR pilot project, we propose to run a proof-of-concept pilot trial to evaluate the effect of the targeted high-definition transcranial direct current stimulation (HD-tDCS) on mitigating the muscle synergy impairment. This study will determine the effect of the proposed targeted HD-tDCS on reducing the upper limb motor impairment, via a pilot trial with a randomized, double-blinded, sham-controlled cross-over design.

### A. Specific Aims

Stroke is the leading cause of serious, long-term disability. Three months after a stroke, 80% of individuals with moderate to severe stroke report movement impairment on the side of the body contralateral to the lesioned hemisphere. The specific movement impairments include a loss of fine motor control with the emergence of highly stereotyped patterns of coarse, multi-joint movements, clinically known as muscle synergies. Despite the development of many interventions for movement recovery post-stroke, rehabilitation treatments are minimally effective to the muscle synergy impairment in more impaired individuals. Treatment advances have been hampered by our poor understanding of neural plasticity post-stroke and the overall lack of lack of precise intervention in neurorehabilitation. Thus, our long-term objectives are to 1) improve the understanding of the underlying neurobiological mechanism of neural plasticity that drives the recovery of motor function; 2) develop targeted interventions that improve stroke rehabilitation in more impaired individuals.

As a result of damage to the corticospinal tract in the lesioned hemisphere, there is evidence of upregulation of cortico-reticulospinal tract excitability in the contralateral side (i.e., the opposite side to the lesion). Both animal and human studies (including the PI [name]'s multi-sites R21 study) in stroke suggest and support the critical role of maladaptive use of the contralateral cortico-reticulospinal tract to post-stroke movement impairments, specifically, the presence of spasticity exhibited by upper extremity muscle synergies. Previous studies applying *transcranial magnetic stimulation* (TMS) to patients after stroke demonstrated that the use of the contralateral cortico-reticulospinal tract requires cortical input from the premotor cortex at the non-lesioned hemisphere. These studies provide potential targets of facilitating the damaged corticospinal tract (via the primary motor cortex) and/or inhibiting the contralateral cortico-reticulospinal tract (via the premotor cortex) for intervention.

In this project, we propose to run a proof-of-concept trial to evaluate the effect of the targeted HD-tDCS on mitigating the motor impairment, via the following two specific aims.

**Aim 1. Demonstrate the feasibility of stroke subject recruitment and retainment.** Our pilot power analysis determined that at least 40 stroke patients will be needed in a full R01 trial. We **hypothesize** that our experimental site at the OUHSC campus has the full ability to recruit 12 eligible patients in one year and retain most of them to complete this trial (detailed in Aim 2).

**Aim 2. Determine the effect of the targeted HD-tDCS on reducing the upper limb motor impairment.** We hypothesize that: 1) facilitating the ipsilesional primary motor cortex will improve the function of the damaged corticospinal tract and therefore, reduce upper limb muscle synergies. 2) inhibiting the contralateral premotor cortex will reduce the maladaptive use of the cortico-reticulospinal tract and thus, also reduce impairment. This randomized, double-blinded, sham-controlled cross-over study will include the anodal HD-tDCS targeting the **ipsilesional primary motor cortex (Aim 2a)**, and the cathodal HD-tDCS over the **contralateral premotor cortex (Aim 2b)**, compared to sham stimulation. We will use a subset of Fugl-Meyer Upper Extremity assessment which is mainly related to the muscle synergies as the primary outcome measure. The TMS-induced motor-evoked potentials (MEP) will be measured to determine the use of ipsilesional corticospinal tract and the contralateral cortico-reticulospinal tract, with the MEP latency as the secondary outcome measure. Resting-state EEG will also be obtained to have the *brain symmetry index* as the third outcome measure for evaluating the acute effect of HD-tDCS on brain plasticity.

### B. Background and Significance

Stroke survivors account for 795,000 adults per year and approximately 7 million individuals living in the US (data from CDC and AHA websites). In stroke rehabilitation research, individuals exhibiting moderate-to-severe upper limb impairment after stroke are underserved and under-investigated. Reviews of existing studies indicate that treatments are minimally in improving of upper limb function(12). Moreover, constraint-induced therapy, a well-established clinical technique, requires a large dosage (30-40 hours/week) that is not always feasible in the current healthcare climate nor can it be used in individuals with more severe motor impairment(12). New interventions are needed that can easily translate to the clinic. Improved intervention strongly relies on our understanding of neural circuitry changes in the motor system after a stroke and how they could be positively and specifically influenced by neuro-rehabilitation technology. Previous studies (including the PI's R21 study(3-5)) found that post-stroke muscle synergy impairment is associated with increased recruitment of the contralateral cortico-reticulospinal tract, following damage to the corticospinal tract at the lesioned side(2, 6) (Fig.1). This finding provides potential neuro-targets to reduce muscle synergies, i.e., facilitating the use of the lesioned corticospinal tract or inhibiting the recruitment of the contralateral cortico-reticulospinal tract. This pilot study will provide the first preliminary data to evaluate the effect of our novel targeted HD-tDCS intervention on reducing upper limb muscle synergies. **This proposal is significant because it targets patients who have had strokes and continue to experience muscle synergy impairment with limited options for improving upper limb movement.**

### C. Preliminary Studies/Progress Report

The contact PI [name] has collected pilot data from both his previous institute Northwestern Medicine, as well as in his current Tulsa lab (OU #IRB 12550). The data demonstrated the feasibility of proposed HD-tDCS technology, showing both anodal (over the ipsilesional primary motor cortex) and cathodal (over the contralateral premotor cortex) HD-tDCS reduced the expression of muscle synergies (Fig. 2). The anodal HD-tDCS reduced the latency of MEP of the damaged corticospinal tract while the cathodal HD-tDCS increase the latency of the MEP of the contralateral cortico-reticulospinal tract. Thus, the previous pilot data support our hypotheses that 1) facilitating the ipsilesional primary motor cortex will improve the function of the damaged corticospinal tract and enhance upper limb movement. 2) inhibiting the contralateral premotor cortex will reduce the maladaptive use of the cortico-reticulospinal tract and reduces the synergy impairment.

[figure not shown]

Fig. 1. Reduced expression of muscle synergies after the targeted HD-tDCS. A1-3 Anodal, C1-2 Cathodal.

### D. Research Design and Methods (What, When, How, Where)

The statistical analysis of our preliminary data indicated that 40 stroke participants are required to ensure the detection of the significance of our results in a complete trial. We will screen up to 50 patients to ensure we can enroll at least **12 stroke** participants in the first year as the pilot sponsored by OSCTR pilot grant. The participants living around the Oklahoma City area (main site) will be asked to come to:

- OU Physician Neurology Clinic [name] (the primary site).
- College of Allied Health at the University of Oklahoma Health Sciences Center located at [name] (the secondary site)

Baseline standard clinical screens including the Fugl-Meyer Motor Assessment (Upper Extremity Portion) will be conducted prior to any intervention trials.

**Overall Overview of Trial Design.** This **sham-controlled cross-over study design** will include three visits: 1) anodal stimulation targeting ipsilesional hemisphere, 2) cathodal stimulation at the contralesional hemisphere, 3) sham stimulation. The sequence of the stimulations will be **randomized and double-blinded**. After each intervention, there will be a 2-week **wash-out period** (minimum) prior to providing the next intervention in the sequence. Each visit will last up to 3 hours including the preparation time and breaks.

We will use neuro-navigation high-definition tDCS (NNG HD-tDCS) to target specific brain regions in a novel and precise manner. A subject-specific head model will be built to evaluate the effect of lesion size and location on the electrical field of tDCS. The MR images (or CT images) will be used to build these subject-specific head models. The stimulation electrode montage and inter-electrode distance will be carefully examined by computer simulation to determine the optimal setup and dosage for NNG HD-tDCS. Based on our pilot test, the stimulation dosage will be set as 2 mA, 20 min, the dosage for best-influencing neuroplasticity according to the safety guidelines of HD-tDCS(13,14).

**Assessments and Outcome Measures.** The following assessments will be performed for baseline, pre- and (immediate) post-intervention time frames. The Fugl-Meyer-Upper Extremity (FM-UE) assessment Part A - mainly related to the muscle synergies and serves as the primary outcome measure. This subset FM-UE assessment increases the sensitivity of the measure and reduces the test time from 30 mins (full assessment) to 10 mins. The TMS-evoke motor-evoked potentials (MEP) will be measured to determine the use of the ipsilesional corticospinal and the contralesional cortico-reticulospinal tract, with MEP latency serving as the secondary outcome measure. The single or paired-pulse TMS will be applied at the respective hotspots for the elbow flexor muscle, i.e., Biceps Brachii, over the ipsilesional primary motor cortex (from which the corticospinal tract originates) and contralesional premotor cortex (from which the cortico-reticulospinal tract originates) with reference to the impaired arm. A 3 min 20 channel Resting-state EEG will also compute the *brain symmetry index* (BSI) as the third outcome measure for evaluating the acute effect of HD-tDCS on brain plasticity. The BSI is defined as the mean of the absolute value of the difference in the mean hemispheric amplitude spectrum; values range from 0 (no asymmetry, normal control) to 1 (maximal asymmetry, more impaired brain function). The total three assessments will last for ~33 min (10 mins subset FU-UE assessment, ~10 mins TMS MEP, and 3 mins EEG recording plus 10 mins procedure time), which will be within the effective period of HD-tDCS. Baseline measurement will be performed at the beginning of the study on the first visit. To ensure there is no carry-over effect, we will compare the outcomes of pre-stimulation measurement with the baseline for each visit.

All recorded data will be de-identified for the analysis. Identifiers might be removed, and the de-identified information may be used for future research without additional informed consent from the subject.

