## **L. Statistical Analysis Plan**

The statistical and power analysis will be led by [name], Assistant Professor of Research in Department of Biostatistics & Epidemiology, Hudson College of Public Health within the University of Oklahoma Health Sciences Center. The obtained preliminary data will refine our power analysis to provide a more precise estimation of sample size for a future full trial. The effect of HD-tDCS is determined by the change in Fugl-Meyer upper extremity Part A score (primary outcome measure), change in Transcranial Magnetic Stimulation (TMS)-Evoke Motor-evoked Potentials (MEP, secondary outcome measures), and change in Brain Symmetry Index (other outcome measures). All statistical analysis was completed using commercial software Statistical Analysis Systems (9.4, SAS, Carey, NC, USA). After checking for and finding no evidence of a non-normal outcome measure distribution, we analyzed the data using generalized estimating equation (GEE) in SAS using PROC GENMOD. The fixed factors are group (anodal, cathodal, sham), time (pre and post intervention), and their interaction, and the random factor is subject ID. This technique uses correlated linear models for each outcome variable (17,18).

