## **M. Data and Safety Monitoring Plan**

*Overall framework for safety monitoring and what information will be monitored.*

The PIs will be responsible for ensuring participants' safety on a daily basis due to the low risk of this mechanistic clinical trial study. All reportable new information (safety data) will be reported to the IRB within 5 days per University policy by the PI following a review with the study team and DSMB. These include but are not limited to new or increased risks, adverse events, serious adverse events, non-compliance with IRB policy, researcher error/protocol violation, and unresolved participant complaints.

Research data will be monitored for completeness every week. The RedCap™ (Research Data Capture) system will be utilized to store all patient demographic information (coded), clinical assessment scores, and all processed data via encrypted university computers. The raw/unprocessed data be coded with a unique patient identifier and stored offline on an encrypted and password protected laboratory computer and backed up to secure online storage through the Shared Services File Storage Service managed by OU/OUHSC IT. Raw data on the computer cluster will be accessible only to study investigators.

*Frequency of monitoring plans for interim analysis and stopping rules.*

A monthly summary of reportable new information (safety data) will be made by the Clinical Research Coordinator (covered by the subcontract to OUHSC), in collaboration with team members in the project and then reviewed by the PIs. Raw research data will be reviewed weekly by the study investigators for organization, completeness, and confirmation of backup. Data quality issues, if any, will be discussed with the investigators and recommendations will be made for immediate solutions by the investigators. An interim analysis will be conducted on research data and directly available to the Program Officer on request. Due to the low risk of the proposed study, minimal adverse events are expected, and no 'a priori' stopping rules will be assigned.

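### Does one sham visit serving two stimulation sites, with sham placement and rater masking unstated, undermine the double-blind claim?

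*Combined protocol and SAP*

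**What the plan says.** Aim 2 in section A of the combined protocol and SAP sets out the design: "This randomized, double-blinded, sham-controlled cross-over study will include the anodal HD-tDCS targeting the" motor cortex on the lesioned side (Aim 2a), and cathodal stimulation over the premotor cortex on the other side (Aim 2b), each compared with sham. Section C describes the same two placements in the pilot data: "showing both anodal (over the ipsilesional primary motor cortex) and cathodal (over the contralateral premotor cortex) HD-tDCS reduced the expression of muscle synergies".

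Section D, under the overview of the design, gives three visits: "1) anodal stimulation targeting ipsilesional hemisphere, 2) cathodal stimulation at the contralesional hemisphere, 3) sham stimulation". It says that the order is randomised and double-blinded, with at least two weeks between interventions. On placement it says "The stimulation electrode montage and inter-electrode distance will be carefully examined by computer simulation"; sham is not mentioned there.

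On measurement, section D says "The following assessments will be performed for baseline, pre- and (immediate) post-intervention time frames". The primary outcome is Fugl-Meyer Upper Extremity Part A. For the secondary outcome, "The single or paired-pulse TMS will be applied at the respective hotspots for the elbow flexor muscle", over both the lesioned-side motor cortex and the opposite premotor cortex. Resting EEG uses 20 channels.

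Section L carries one sham level into the model: "The fixed factors are group (anodal, cathodal, sham), time (pre and post intervention), and their interaction".

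**The concern.** Most sham-controlled stimulation trials have one target, and sham is given at that target. Here there are two targets and one sham visit. If electrodes are fitted only at the site being treated, sham cannot look like both active visits, and anyone who knows where sham is given could recognise the other site as active.

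The primary outcome is scored by a rater immediately after stimulation, so a rater who had seen the electrodes might carry an expectation into the score. A participant might also perform differently when sure of receiving active treatment. If the sham site were fixed, this would fall on only one of Aims 2a and 2b. A reader of the protocol cannot tell whether the blind covers both comparisons, one of them, or the rater. MEP latency and the brain symmetry index are instrument measures and less exposed. Aim 1, on recruitment and retention, is not touched.

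**Working it through.** **Inputs.** Three visits, one of them sham (section D); two active sites (section A, Aim 2); one sham level (section L); 12 participants (sections A and D; section D says at least 12). The plan states no figure on blinding, so there is none to reproduce.

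**1. What is silent.** Sections D and L are the natural places for the sham montage, the blinded roles and rater masking. Neither gives them, and nor does any other section available. The text between sections J and L was not available, so what it says is unknown.

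**2. Site matching.** Active-sham pairs within participants: 12 × 2 = 24.
- One montage per visit, sham at one of the two active sites: each participant has one matched pair, so 12 × 1 = 12 of 24. This holds whether the sham site is fixed or varies between participants. Fixed puts all 12 matched pairs in one aim. Varied spreads them over both, 6 and 6 only if allocation is balanced.
- Both montages fitted at every visit: 24 of 24.

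**3. What a site cue could reveal.** Assume one montage per visit and six equally likely orders.
- An observer who sees the site and knows where sham is given: belief that the visit is active is 1 at the unmatched active visit and 1/2 at sham, a gap of 50 points. An observer who does not see the site, or does not know the sham site, has a gap of 0.
- A participant who knows the three-condition design but not the sham site (each site equally likely), and who remembers sites perfectly across visits, has these beliefs over the six orders:
  - Unmatched active visit: (3/4 + 1 + 2/3 + 2/3 + 1 + 3/4) / 6 = 29/36, or 81%.
  - Sham visit: (1/2 + 1/2 + 1/2 + 3/4 + 2/3 + 2/3) / 6 = 43/72, or 60%.
  - Gap: 58/72 − 43/72 = 15/72, or 20.8 points, with certainty in 2 of 6 orders (4 of 12 participants on average).
- If half of participants track site, the gap is 0.5 × 20.8 = 10.4 points; if none do, it is 0.

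Moving sham to the other site swaps the two active conditions and leaves the gap unchanged, so the same calculation covers a sham site that varies between participants.

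**4. Would recording treatment guesses help?** With 12 participants, 8 guesses of active out of 12 has an exact 95% interval of 35% to 90%. In an exact paired sign test, six discordant pairs all in one direction give 2 × (1/2)^6 = 0.031, and five give 2 × (1/2)^5 = 0.0625, so at least six are needed. If guesses are independent and made with probability equal to belief, power at the 5% level is 61% for the 50-point gap and 6% for the 20.8-point gap.

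**5. What the analysis would do differently.** Nothing. The group-by-time model in section L, the outcomes and the number enrolled are the same under any of these sham arrangements.

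**The case for a change.** The best case for asking for a change is that this is more than a reporting preference. The two-site, one-sham structure makes the sham montage matter here in a way it does not in a one-target trial. The primary outcome depends on a rater, and section L says that the data will refine the power calculation for a full trial, so it is useful to know which contrast was blinded and for whom. The cost looks small: a few sentences, and a field in the database where, under section M, the "system will be utilized to store all patient demographic information (coded), clinical assessment scores, and all processed data" are already kept.

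Two parts of this stand. The silence is real in the text available, and under a single-site sham one active visit per participant is unmatched. A reader may fairly ask the sponsor where sham was placed and who scored the Fugl-Meyer.

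The step from silence to harm does not stand. It needs one montage per visit, and then an observer who sees the site and knows where sham is given, or a participant who tracks placement across visits at least two weeks apart. The documents support none of these conditions. Two ordinary arrangements, fitting both montages every time or keeping the rater away from set-up, deal with the rater's site cue, and the plan excludes neither. TMS at both hotspots and EEG before and after stimulation mean that both scalp areas are handled at every visit, which may blur the cue, though it need not hide where the stimulation electrodes sit. The 50-point and 20.8-point figures are upper bounds on belief under those conditions; they are not estimates for this trial and say nothing about the size of any Fugl-Meyer bias.

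**Conclusion.** No change to the plan follows. The protocol omits operating detail that the team must settle in order to run the visits at all and can describe when it reports. The omission does not show a design fault.

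Its size, on design alone: 12 of 24 active-sham pairs are site-matched if a single montage is worn per visit, and 24 of 24 if both are; the documents do not choose between these. The effect on belief runs from 0 up to the bounds above, and there is no basis for any figure on the Fugl-Meyer scale. Recording guesses would detect the smaller bound with only 6% power, so it would not resolve the question.

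This rests on 12 participants, equally likely orders, and the text available, which lacks the part between sections J and L. If sham proves to have been given at a single site, fixed or varied, readers should interpret the unmatched comparison or comparisons with that in mind. That is a matter for interpreting a proof-of-concept result and leaves the analysis as planned.

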#### **G. Inclusion / Exclusion Criteria**

Stroke participants should have sustained an ischemic unilateral lesion (confirmed by the most recent clinical or radiological reports) at least 3 months prior to participation in this project. The following inclusion criteria will be applied to the stroke participants: 1) Paresis confined to one side, with moderate to severe motor impairment of the upper limb (Fugl-Meyer upper extremity scores of 10-40); 2) Absence of muscle tone abnormalities and motor or sensory impairment in the unimpaired limb; 3) Absence of severe wasting or contracture or significant sensory deficits in the paretic upper limb; 4) Absence of severe cognitive or affective dysfunction that prevents normal communication and understanding of consent or instruction; 5) Absence of severe concurrent medical problems (e.g. cardiorespiratory impairment); 6) Capacity to provide informed consent; 7) Not using a pacemaker, 8) No metal implants in the head 9) No known adverse reaction to TMS and tDCS; 10) Capacity to provide informed consent; 11) Not pregnant.

We are not performing specific assessments since the main goal of our study is to investigate the motor function and movement recovery after stroke. If participants can communicate with the researcher, and understand the procedures well and have the ability to consent, they meet this criterion (5). Stroke participants using a wheelchair or other assistive mobility devices are eligible to participate if they meet the inclusion criteria (1)-(11).

There may be circumstances under which participation may be terminated by the investigator without consent. The examples may include but not limited to:

- The investigator feels that it is in the individual's best interest.
- The individual's condition worsens, or any new condition makes the individual no longer qualified for this study.
- New information becomes available resulting in the individual no longer meeting the inclusion criteria.
- The individual fails to follow study requirements.
- The study is stopped by the sponsor.

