### **J. Risks and Benefits**

The self-adhesive surface electrodes used to record muscle activity (EMG) may produce minor irritation of the skin; there is also the possibility of an allergic reaction to the electrode paste. The possibility of irritation will be minimized by cleaning the skin with alcohol before and after the application of the electrodes. There is a similar possibility of scalp irritation due to a reaction to the use of EEG/tDCS electrodes.

The tDCS may cause transient itching and tingling at the beginning of the delivery of stimulation due to the change of voltage/current as it ramps up to the targeted intensity. However, most people reported that these are very mild and fade quickly. A small number of participants may report moderate fatigue, particularly during, but not after stimulation. Minor scalp skin irritation may occur but will be minimized by screening participants who self-report having sensitive skin (based on the tDCS Safety Screening Tool (TSST)(16)).

If stroke patients participate in this study, possible benefits may include an improved ability to control their paretic arm during movement tasks. Benefits may or may not continue after the research has ended. Possible benefits to others include an enhanced understanding and treatment of movement disturbances following a stroke.

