***Management and reporting of adverse events and serious adverse events.***

Upon first knowledge of an adverse event or serious adverse event (also including any reportable new information), the event will be reported to the clinical research coordinator. After reviewing with the PIs, the OUHSC clinical research team, and relevant personnel, the clinical research coordinator will generate the IRB report and queue for review and submission by the PI to the IRB within 5 days per University/IRB policy. A copy will also be sent to the Office of HRPP. The study PI will report all adverse and serious adverse events to the NIH within the same time frame. The PI will have weekly meetings with team members to review all reportable new information.

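### The available text schedules no adverse-event question at any visit and no contact after a participant's last stimulation, so safety data rest on unsolicited reports

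*Combined protocol and SAP*

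**What the plan says.** **Visits.** Section D (Overall Overview of Trial Design) states that the study "will include three visits: 1) anodal stimulation targeting ipsilesional hemisphere", then cathodal stimulation and sham, with the sequence randomized. The gap between visits is set as follows: "After each intervention, there will be a 2-week wash-out period (minimum) prior to providing the next intervention in the sequence". No interval or contact is defined once there is no next intervention.

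**Measurements.** Section D (Assessments and Outcome Measures) gives the timing: "The following assessments will be performed for baseline, pre- and (immediate) post-intervention time frames". The list is Fugl-Meyer Part A, motor-evoked potentials and resting EEG, about 33 minutes in total. Pre-stimulation values at each visit are compared with baseline to look for carry-over.

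**Named risks.** Section J names itching, tingling, fatigue and scalp irritation from tDCS. It places itching and tingling at the start of stimulation, and on fatigue says: "A small number of participants may report moderate fatigue, particularly during, but not after stimulation". The one safety instrument it mentions is used beforehand, to screen for sensitive skin.

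**Capture.** Section M starts the handling of an event "Upon first knowledge of an adverse event or serious adverse event". Its weekly meetings and monthly summaries review reports already received; they are not contacts with participants.

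**Early termination.** Section G lets the investigator end participation. One example ground is: "The individual's condition worsens, or any new condition makes the individual no longer qualified for this study". No exit contact is described.

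**The concern.** Two gaps lie side by side. First, the plan names the effects it expects from tDCS but does not ask about them at a set time in a set form. A low count could then mean few events or few questions, and the plan gives no way to tell which. Second, after visits 1 and 2 the participant comes back and the Fugl-Meyer Part A is repeated before stimulation, so a lasting loss of arm function would be measured. After the last stimulation nobody is scheduled to look. The same holds for someone who leaves after visit 1 or 2.

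At stake is the quality of the safety information that the pilot hands to the full trial it is meant to support, and of the adverse-event results that Section N undertakes to post on ClinicalTrials.gov. Section M expects few adverse events and sets no stopping rules in advance; unsolicited reports are a weak test of that expectation.

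**Working it through.** **The plan's own figure.** Scheduled observation after stimulation: 10 min (Fugl-Meyer subset) + 10 min (motor-evoked potentials) + 3 min (EEG) + 10 min (procedure time) = 33 min. This agrees with the stated total. No other scheduled observation follows a stimulation except the next visit.

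**Inputs.** 12 participants: Section A aims to "recruit 12 eligible patients in one year and retain most of them to complete this trial". Three stimulation visits each (Section D). Randomized order, with no list of sequences or blocking given; the Abstract says only that the effect is determined "via a pilot trial with a randomized, double-blinded, sham-controlled cross-over design". No number is attached to retention, so early stops from 0 to 6 are assumed here.

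**Step 1: solicited events.** No adverse-event item appears among the scheduled measurements at any visit. For symptoms that only a question would reveal, the gap covers all 12 × 3 = 36 exposures.

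**Step 2: exposures with no later scheduled encounter.** Each participant has exactly one last exposure. With d1 participants stopping after visit 1 and d2 after visit 2:

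share = 12 / (36 − 2·d1 − d2)

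| d1 | d2 | Exposures | Share |
|---|---|---|---|
| 0 | 0 | 36 | 12/36 = 33.3% |
| 0 | 1 | 35 | 12/35 = 34.3% |
| 1 | 0 | 34 | 12/34 = 35.3% |
| 2 | 2 | 30 | 12/30 = 40.0% |
| 3 | 3 | 27 | 12/27 = 44.4% |

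One third is therefore the minimum. This figure concerns what a return visit could reveal without a question, chiefly a lasting change in the Fugl-Meyer Part A score.

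**Step 3: does the loss fall unequally on the conditions?** Under randomized order each condition has probability 1/3 of being last, so the expected number is 12 × 1/3 = 4 for each. If the six possible sequences are each used twice, the split is exactly 4/4/4: 8 of 24 active exposures and 4 of 12 sham exposures, both 33.3%. If each order is drawn independently, the probability of an exact 4/4/4 split is 12!/(4!·4!·4!)/3^12 = 34,650/531,441 = 6.5%. The probability that some condition is last six or more times is 52.8% (exact multinomial). Imbalance is thus likely under simple randomization, but it has no systematic direction.

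**Step 4: effect of one contact after the last stimulation.** If all complete and are reached, exposures without a later scheduled contact fall from 12/36 to 0/36.

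**The case against.** The case against has real force.

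- **Reporting does not stop at visit 3.** Section M gives no end date and covers all adverse events and unresolved complaints. What is absent is a scheduled contact, not every route by which an event could become known. This stands.
- **The named effects are mostly immediate.** Section J places itching, tingling and fatigue at onset or during stimulation, when staff are present. Of the effects it names, only scalp irritation could readily appear later, and delayed loss of arm function is not listed as a risk. For most named effects the missing question at the visit therefore matters more than the missing call. Against this, Section J also says that benefits may or may not persist after the research, so the plan does not assume that every effect ends with the visit.
- **A worsening that leads to termination is already known** to the investigator and would be reported under Section M. Only later or separate events could be missed in that person.
- **The stakes are modest.** The study is described as low risk, the aims are feasibility and motor effect, and Section L plans no comparison of adverse events by condition.

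A reader might also infer that harms by condition are confounded with order, or that counts for anodal, cathodal and sham cannot be compared. The documents do not support either. The sequence is randomized, so the loss of follow-up is equal in expectation across conditions, and what remains is chance imbalance among 12 people.

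Finally, the front matter and the text between Sections J and L were not available for review. An adverse-event form or an exit contact may be described there.

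**Conclusion.** The point holds as a minor one. In the available text no visit has a scheduled adverse-event question, and no contact is scheduled after a participant's last stimulation, whether that is visit 3 or an earlier visit followed by termination. Symptoms rely on unsolicited reports for all 36 planned exposures. At least 12 of 36 (33.3%) have no later scheduled encounter; the share reaches 40.0% if two participants stop after visit 1 and two after visit 2.

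The likely consequence is an under-count of harms overall. The comparison between conditions is not biased in expectation, provided that early stopping does not depend on the condition received; the documents give no figure on that. The shares assume that all 12 receive at least one stimulation. The probabilities for chance imbalance assume independent draws of the order, which the plan neither states nor excludes.

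**What to change.** 1. **Sections D and M:** add one short fixed list (itching, tingling, fatigue, scalp or skin reaction, change in arm function, any other event). Ask it in the same words immediately after stimulation at every visit, sham included, and before stimulation at visits 2 and 3.
2. **Section D, with a cross-reference in Section G:** add one telephone contact about 2 weeks after the last stimulation received, using the same list, for completers and for anyone whose participation ends early. Two weeks matches the plan's own minimum gap between interventions. The call gives self-report only and does not replace a scored Fugl-Meyer.
3. **Section L:** report events by condition, with exposures as the denominator.

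If the text not available for review already contains such a form or contact, a cross-reference from Sections D and M is enough.

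**Cost:** about 12 calls, a few minutes within each visit of up to 3 hours, one REDCap form and a short amendment, using the existing coordinator. More mild events will be recorded than under unsolicited reporting.
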